#### 3.1.4 Summary Statistics

All study-collected data will be summarized by treatment group for the appropriate analysis population, using descriptive statistics, graphs, and/or raw data listings. Descriptive statistics for continuous variables will include n (number of non-missing values), mean, standard deviation, first quartile (Q1), median, third quartile (Q3), minimum, and maximum. Analysis of categorical variables will include frequency and percentage.

#### 3.1.5 Handling of Dropouts and Missing Data

Missing data will be imputed only in the context of sensitivity analysis as described in section 3.4.1.

## 3.2 Analysis Populations

#### 3.2.1 Full Analysis Set (FAS)

The Full Analysis Set (FAS) will consist of all randomized patients who take at least 1 dose of study drug and have a baseline fasting TG measurement. Analyses of primary and secondary efficacy endpoints will be performed on the FAS.

#### 3.2.2 Per-Protocol Set (PPS)

The Per-Protocol Set (PPS) will include all FAS patients without any major protocol deviations and who have baseline and Day 28 endpoint fasting serum TG measurements. Major protocol deviations will be confirmed prior to database lock. Major protocol deviations that may impact the primary efficacy assessment may include but are not limited to:

- Failed to meet eligibility criteria
- Discontinued study drug
- Had study drug compliance <80% or >120%
- Took a restricted concomitant medication

A list of patients with major protocol deviations leading to exclusion from the PPS will be finalized prior to database lock.

The Per-Protocol Set will be the primary analysis population.

#### 3.2.3 Safety Analysis Set

The Safety Analysis Set will include all randomized patients who receive at least 1 dose of randomized study drug. All safety analyses will be conducted on the Safety Analysis Set.

# 3.3 Subject Data and Study Conduct

#### 3.3.1 Subject Disposition

Counts and percentages of patients who were screened (signed informed consent), discontinued early during screening (screen failures), and randomized will be summarized in

total based on all screened patients. Primary reasons for screen failure will also be summarized. Patients whose primary reason for screen failure was due to Coronavirus Disease 2019 (COVID-19) will also be summarized.

Counts and percentages of patients who were randomized, treated, discontinued early from the study, and completed the study will be summarized by treatment and in total based on all randomized patients. Primary reasons for early discontinuation will also be summarized. Patients whose primary reason for early discontinuation was due to COVID-19 will also be summarized.

## 3.3.2 Protocol Deviations

Protocol deviations are defined in the Protocol Deviation Plan and classified as CSR reportable or CSR non-reportable. All CSR-reportable protocol deviations will be listed.

#### 3.3.3 Analysis Populations

Counts and percentages of patients in each analysis population will be summarized by treatment and in total based on all randomized patients.

#### 3.3.4 Demographic and Baseline Characteristics

The following demographic and baseline characteristics will be summarized:

- Age (years) and age categories (<65 years, ≥65 years)
- Sex (Male or Female)
- Age categories by sex (Age categories include <12 years, 12 <18 years, 18 <65 years, and ≥ 65 years).
- Childbearing potential
- Race
- Ethnicity
- Height (cm)
- Weight (kg)
- Body mass index (BMI) (kg/m^2)
- Statin Use (Yes, No)
- •

Demographic and baseline characteristics will be summarized with descriptive statistics or counts and percentages of patients as appropriate by treatment and in total for all randomized patients and each defined analysis population.

#### 3.3.5 Medical History

Medical history will be coded to system organ class and preferred term using the Medical Dictionary for Regulatory Activities (MedDRA) version 23.0, March 2020. Dictionary updates will be applied at the time of database lock to the latest version available. Counts and percentages of patients with medical history by system organ class and preferred term will be summarized by treatment and in total based on all randomized patients.

#### *3.3.6 Concomitant Medications*

Concomitant medications will be coded to anatomical therapeutic chemical (ATC) class and preferred term using the WHODrug Dictionary Global B3, September 2019. Dictionary updates

will be applied at the time of database lock to the latest version available. For summary purposes, medications will be considered prior medications if they were stopped prior to the first dose of study drug and concomitant medications if they were taken at any time after the first dose of study drug (i.e. started prior to the first dose of study drug and were ongoing or started after the first dose of study drug).

If a medication has incomplete start or stop dates, dates will be imputed to determine whether a medication should be considered prior or concomitant. If a medication start date is incomplete, the first day of the month will be imputed for missing day and January will be imputed for missing month. If a medication stop date is incomplete, the last day of the month will be imputed for missing day and December will be imputed for missing month. Incomplete start and stop dates will be listed as collected without imputation.

Counts and percentages of patients taking prior and concomitant medications by ATC class and preferred term will be summarized by treatment and in total based on the Safety Analysis Set.

## 3.3.7 Study Drug Exposure and Compliance

Days of exposure to study drug will be calculated as date of last dose of study drug – date of first dose of study drug + 1. Note that the exposure calculation is intended to describe the length of time a patient was exposed to study drug and therefore does not take study drug interruptions into account. Days of exposure to study drug will be summarized by treatment based on the Safety Analysis Set with descriptive statistics.

Percent compliance to the study drug regimen will be calculated as follows:

For patients randomized to the K-877-ER arm, compliance will be calculated as:  $\frac{Total \ number \ of \ tablets \ dispensed - Total \ number \ of \ tablets \ returned}{Date \ of \ last \ visit - Date \ of \ randomization + 1} x \ 100$ For patients randomized to the K-877-ER arm, compliance will be calculated as:  $\frac{Total \ number \ of \ tablets \ dispensed - Total \ number \ of \ tablets \ returned}{2 \times (Date \ of \ last \ visit - Date \ of \ randomization + 1)} x \ 100$ For patients randomized to the K-877-IR arm and completed the 28-day treatment period, compliance will be calculated as:

$$\frac{Total number of tablets dispensed - Total number of tablets returned}{(2 * (Date of last visit - Date of randomization + 1)) - 1} x 100$$

For patients randomized to the K-877-IR **and a** arm and discontinued prior Day 28, compliance will be calculated as:

$$\frac{Total number of tablets dispensed - Total number of tablets returned}{2 * (Date of last visit - Date of randomization + 1)} x 100$$

If study drug is not returned, the number of tablets returned will be considered 0 for the compliance calculation.

Percent compliance to the study drug will be summarized by treatment based on the Safety Analysis Set with descriptive statistics and with counts and percentages of patients with compliance in the following categories:

- <80%
- 80-120%
- >120%

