5.5 Drug Supplies

5.5.1 Formulation and Packaging

The K-877-ER tablet is a round, 7.6 mm diameter, white, film-coated tablet for oral administration, containing pemafibrate.

The K-877-ER tablet contains the following excipients:

| The K-877-IR tablet is a round, 7.1 mm diameter, | white, film-coated tablet for oral |
|--|------------------------------------|
| administration, containing pemafibrate. | |

K-877-IR tablet contains the following excipients:

Drug packaging will be completed by an product will be distributed to sites by

Investigational

Study drugs will be packaged in clear polyvinylidene chloride/aluminum foil blisters within a child-resistant card. Patients will receive a complete supply of study drug on Day 1.

Study drugs will be labeled according to country/state/province-specific requirements. For example, the label will include the following information:

- Name and address of Sponsor (i.e., KRI);
- A study reference code (e.g., protocol number) allowing identification of the investigational site and Investigator;
- Route of administration, quantity of dosage units, and pharmacological form as appropriate;
- Lot number;
- Directions for use;
- The statement "Caution New Drug Limited by Federal (United States) Law to Investigational Use";
- The statement "Keep out of reach of children"; and
- The storage conditions.

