5.5.3 Study Drug Administration

Patients will receive oral doses of K-877-ER **K**-877-ER **K**-877-ER **K**-877-ER **K**-877-IR **K**-877-IR **K**-877-IR **K**-877-IR treatment group will receive only the morning dose on Day 28. Study drug will be administered in the fed state at 0 hour with 240 mL of room temperature tap water. Within 30 minutes prior to study drug administration on Days 1 and 28, **M** patients confined to the clinical site will be administered a meal that is part of a daily diet containing approximately 2300 to 2500 calories, less than 60% carbohydrates, and less than 25% fat. On Days 1 and 28, **M** patients will not receive any oral

fluids other than those used to administer the dose for 1 hour before and 1 hour after dosing on Days 1 and 28.

patients will remain standing or sitting upright for 4 hours after dosing, except as required by any study procedure. Patients in the K-877-IR **dote** treatment group will receive an evening dose after a meal.

Diet and dosing time should remain consistent for all doses throughout the study. Patients will be instructed by the site to follow dosing instructions on the drug packaging and to return all used, partially used, and unused study drug materials on Day 28.

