5.5.4 Treatment Compliance

Study drug will be dispensed in excess of the amount required for the study. Patients will be instructed to bring all unused study drug to each visit. At both visits, Days 14 and 28, the patient will be asked whether there have been any problems with taking the medication, and the Investigator will record any significant departure from the dosing instructions (e.g., misuse or overdose) as a protocol deviation. A Special Situations Report may need to be completed (see Section 8.6 for additional details about Special Situation Reports). A record of the number of tablets dispensed, taken, and returned for each patient must be documented on the Drug Accountability Log and eCRF. Compliance will be assessed from information recorded in the eCRF, including study drug count and the start and end date of study drug. Patients will be considered compliant if they have taken between 80% and 120% of the intended regimen.

During the treatment period, if compliance is not between 80% and 120%, inclusive, the patient will be counseled about the importance of compliance with the regimen. See Section 5.5.3 for study drug administration information.

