9.1.2 Per-Protocol Set

The Per-Protocol Set will include all FAS patients without any major protocol deviations and who have baseline and Day 28 endpoint fasting serum TG measurements. Major protocol deviations will be confirmed prior to database lock. The following criteria will be used to determine major protocol deviations prior to unblinding of treatment allocation:

- No violations of eligibility criteria;
- No discontinuation of study drug;
- Patients did not take any prohibited concomitant medications during the study;
- Study drug compliance within 80% to 120%; and
- No other substantial protocol deviations.

[figure not shown]
The Per-Protocol Set will be the primary analysis population.

| | |
|------|--|
| | |
| | |
| | |
| | |
| | |
| | |
| | |
| | |
| | |
| | |

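### Counting unreturned tablets as taken makes the 80–120% compliance criterion blind to under-dosing in patients who return nothing, and with enough overage it fails fully adherent ones

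*SAP*

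**What the plan says.** SAP 3.3.7 divides tablets dispensed minus tablets returned by tablets expected up to the last visit. For missing returns it states: "If study drug is not returned, the number of tablets returned will be considered 0 for the compliance calculation".

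The protocol supplies the context:

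- Section 5.5.1: "Patients will receive a complete supply of study drug on Day 1".
- Section 5.5.4: "Study drug will be dispensed in excess of the amount required for the study". The size of the excess is not given.
- Section 5.5.4 defines a compliant patient by the share of the regimen taken, and requires that count: "A record of the number of tablets dispensed, taken, and returned for each patient must be documented on the Drug Accountability Log and eCRF".
- Section 5.5.3 tells patients to "return all used, partially used, and unused study drug materials on Day 28".

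Compliance from 80% to 120% is among the Per-Protocol Set (PPS) criteria in Protocol 9.1.2. SAP 3.2.2 lists values outside that range as a possible major deviation, and adds: "The Per-Protocol Set will be the primary analysis population".

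**The concern.** A pack that does not come back says nothing about how many tablets were swallowed. The SAP rule treats it as proof that all of them were, including the spare ones. This departs from Protocol 5.5.4, which defines compliance by intake. It also sits badly with Protocol 8.6, which does not accept an accountability discrepancy alone as establishing an overdose.

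Two errors can follow for a patient who attends Day 28 but returns nothing. One who missed many doses can be kept in the PPS as compliant. One who took every dose can be excluded as over-compliant. Both act on the population that decides non-inferiority. Keeping under-dosed patients weakens the purpose of a per-protocol comparison. Wrongful exclusions use up a small allowance: 30 randomized per group against 26 needed, so four patients.

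Direction matters too. The immediate-release product (IR) is taken morning and evening (SAP 2.2.3), and the protocol expects ER to help adherence (sections 1.1 and 5.2). If under-dosing is more common on IR, keeping such patients would dilute the reference response and make non-inferiority easier to show. That is plausible, but the documents do not allow it to be quantified.

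**Working it through.** The plan states no compliance figure to reproduce, so the check applies its own formulas.

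**Inputs**

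- Dosing days: 28 (schedule of procedures).
- Last visit day L: 25, 28 or 31 (Visit 6 is Day 28 ± 3 days). Day 1 is the day of randomization, so the SAP's day count equals L.
- Expected tablets (SAP 3.3.7): L for one-tablet ER, 2L for two-tablet ER, 2L − 1 for IR completers.
- Overage: not stated. Assumption: ER tablets dispensed = daily tablets × (28 + k), with k whole spare days.

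**Nothing returned**

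With returns set to 0, the score in either ER arm is (28 + k)/L. Tablets taken do not appear in it.

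| Last visit | Lowest score (k = 0) | Largest k not above 120% | First k above 120% |
|---|---|---|---|
| Day 25 | 28/25 = 112.0% | k = 2: 30/25 = 120.0% | k = 3: 31/25 = 124.0% |
| Day 28 | 28/28 = 100.0% | k = 5: 33/28 = 117.9% | k = 6: 34/28 = 121.4% |
| Day 31 | 28/31 = 90.3% | k = 9: 37/31 = 119.4% | k = 10: 38/31 = 122.6% |

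IR behaves the same way. The need is 2 × 28 − 1 = 55 tablets, so with no overage the Day 31 score is 55/(2 × 31 − 1) = 55/61 = 90.2%. At Day 28 the score first exceeds 120% at 67 tablets dispensed (67/55 = 121.8%).

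**Pack returned, one-tablet ER, Day 28**

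The score is tablets taken/28. Taking 22 gives 78.6%, which is flagged; taking 23 gives 82.1%, which passes. The lower limit works here.

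**Same intake, with and without the pack (one-tablet ER, Day 28)**

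| Patient | Pack returned | Nothing returned |
|---|---|---|
| 14 of 28 doses, k = 3 | (31 − 17)/28 = 50.0% | 31/28 = 110.7% |
| 28 of 28 doses, k = 6 | (34 − 6)/28 = 100% | 34/28 = 121.4% |

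The first patient moves from flagged to compliant, and the second from compliant to flagged.

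**The case against.** The strongest reply concerns consequence. The overage is unknown, and at a Day 28 visit an adherent ER patient fails only with six or more spare days. Few patients may be affected: they must attend Day 28 with a fasting triglyceride value, return nothing, and have under-dosed without stopping drug, since discontinuation is a separate exclusion. Patients bring unused drug to each visit, compliance is checked at Day 14 as well as Day 28, and the investigator records significant dosing departures. The SAP's deviation list is open-ended and confirmed before lock, and a separate Protocol Deviation Plan may settle unverifiable counts. The primary analysis is repeated in the Full Analysis Set (FAS). A fixed rule applied alike to all arms is also a recognizable convention.

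Much of this stands as a limit on impact. The over-120% half is conditional on overage, and the number affected could be zero. None of it corrects the score, however, and the under-dosing half needs no overage assumption. The FAS repeat lifts every PPS exclusion at once, so it cannot isolate this one. Case-by-case repair before lock is a weak safeguard in an open-label study, because treatment may be known to those deciding.

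The SAP also leaves the last visit undefined. If it meant the follow-up call, a non-returner could fall below 80% (28/37 = 75.7% at Day 37), but because of the later date and not because of missed doses.

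**Conclusion.** The concern holds. For patients who return nothing, the score in SAP 3.3.7 does not depend on intake. At an in-window final visit it cannot fall below about 90%, so the 80% limit cannot identify under-dosing. This assumes only that at least the required supply was dispensed and that the last visit is Visit 6.

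The upper limit wrongly fails adherent ER patients only when spare supply exceeds 2, 5 or 9 days at a Day 25, 28 or 31 visit respectively; whether it does cannot be told from the documents. The number of patients affected and the effect on the non-inferiority result cannot be determined either. The rule should be corrected before database lock because it feeds a criterion for the primary analysis population. It does not call the design or sample size into question.

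**What to change.** Change the SAP as follows:

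1. Delete the rule in 3.3.7 that sets missing returns to 0.
2. When returns are missing, use the tablets-taken count required by Protocol 5.5.4, provided it was not itself derived as dispensed minus returned.
3. Otherwise set compliance to missing and add a *not assessable* category to the three already listed.
4. State before lock that these patients are not excluded on the 80–120% criterion alone, and record in SAP section 5 how that criterion is applied when compliance is missing.
5. Run the primary analysis with and without them.

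The cost is SAP wording, one table category, minor programming and one extra model run; no protocol amendment is needed. There are limits. The taken count may rest on patient report, and some non-adherent patients may stay in the PPS, including some with large overage whom the present rule would have flagged. The with/without run shows their influence. If no independent count exists and overage is small (five spare days or fewer at a Day 28 visit for ER), PPS membership does not change. The gain is then an honest *not assessable* label and the with/without comparison.

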## 3.4 Efficacy Assessment

Efficacy data will be summarized by randomized treatment based on the PPS. The primary and secondary efficacy endpoints will also be summarized based on the FAS. Descriptive statistics (n, mean, standard deviation [SD], first quartile [Q1], median, third quartile [Q3], minimum, maximum, and 90% CI) for the primary endpoint and secondary endpoints will be summarized by treatment group at baseline and Days 14 and 28. Descriptive statistics for changes from baseline and for percent changes from baseline to each visit will also be summarized.

All available and derived data for the primary and secondary endpoints will be listed for the randomized patients.

Spaghetti plots of individual patient data by treatment and box plots of the percent change from baseline to each post-baseline visit by treatment will be generated for the primary and secondary efficacy endpoints based on the PPS and FAS. Mean  $\pm$  SD of percent change from baseline to each post-baseline visit by treatment will also be generated for the primary and secondary efficacy endpoints based on the PPS and FAS.

#### Secondary Analyses

As a secondary analysis, the primary analysis described above will be repeated in the FAS.

## *3.4.2 Secondary Efficacy Endpoints*

The secondary efficacy endpoints will be summarized and analyzed in the same manner as the primary analysis (Section 3.4.1). Each secondary endpoint will be evaluated using the MMRM model in the PPS where percent change from baseline variable will be used as the dependent or response variable.

The following secondary endpoints will be analyzed:

- TC
- LDL-C
- HDL-C
- Remnant cholesterol (calculated as TC LDL-C HDL-C)
- Non-HDL-C
- Free fatty acids

Analysis of the above secondary efficacy endpoints will also be repeated in the FAS.

## 3.6 Safety Assessment

Safety data will be summarized by actual treatment received (and in total for selected analyses) based on the Safety Analysis Set.

#### *3.6.1 Adverse Events (AEs)*

AEs will be captured from the date of informed consent through study completion. All AEs will be coded to system organ class and preferred term using MedDRA version 23.0, March 2020.

Treatment-emergent adverse events (TEAEs) are defined as AEs that occurred for the first time after the first dose of study drug or existed prior to the first dose and worsened during the treatment period. AE worsening applies to severity, or relationship to study drug.

An overview of AEs will be provided including counts and percentages of patients and event counts with the following:

- Any TEAEs (overall, by maximum severity, and by relationship to study drug)
- Any study drug related TEAEs (overall and by maximum severity)
- •
- Any serious AEs (SAEs)
- Any treatment-emergent serious AEs (TESAEs)
- Any study drug related TESAEs
- Any AEs and TEAEs leading to death
- Any TEAEs leading to study drug discontinuation
- Any TEAEs leading to study discontinuation
- Any TESAEs leading to study drug discontinuation
- Any study drug related TEAEs leading to study drug discontinuation

Counts and percentages of patients and event counts will also be presented by system organ class and preferred term for each of the categories in the overview.

Listings will be presented specifically for SAEs and TEAEs leading to discontinuation of study drug.

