6.4 Treatment Period

Following randomization, assigned study drug will be dispensed to patients. Details of initial visit along with subsequent visits are detailed in the Schedule of Procedures in Appendix A. The Treatment Period begins on Day 1 and concludes on Day 28. Experiments will be required to return to the clinical site on Day 14 (\pm 3 days) and Day 28 (\pm 3 days) for efficacy and safety assessments.

patients will be admitted to the clinical site on Day -1 and will remain until discharged from the clinical site on Day 2. The patients will return to the clinical site on Day 14 (\pm 3 days) for efficacy and safety assessments. On Day 27, the patients will be readmitted to the clinical site and will remain until discharged from the clinical site on Day 29.

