8 SAFETY ASSESSMENTS

8.1 Adverse Events

An AE is defined as any untoward medical occurrence in a clinical investigation subject administered a pharmaceutical product, which does not necessarily have a causal relationship with this treatment. An AE can therefore be any unfavorable and/or unintended sign (including an abnormal laboratory finding), symptom, or disease temporally associated with the use of an investigational medicinal product, whether or not related to the investigational medicinal product. All AEs, including observed or volunteered problems, complaints, or symptoms, are to be recorded on the appropriate eCRF.

AEs, which include clinical laboratory test variables, will be monitored and documented from the time of informed consent until the Follow-Up Telephone Call. Patients should be instructed to report any AE that they experience to the Investigator, whether or not they think the event is due to study treatment. Beginning from the time of informed consent, Investigators should make an assessment for AEs at each visit and record the event on the appropriate AE eCRF.

Wherever possible, a specific disease or syndrome rather than individual associated signs and symptoms should be identified by the Investigator and recorded on the eCRF. However, if an observed or reported sign or symptom is not considered a component of a specific disease or syndrome by the Investigator, it should be recorded as a separate AE on the eCRF. Additionally, the condition that led to a medical or surgical procedure (e.g., surgery, endoscopy, tooth extraction, or transfusion) should be recorded as an AE, not the procedure itself.

Any medical condition already present at the Screening Visit should be recorded as medical history and not be reported as an AE unless the medical condition or signs or symptoms present at baseline changes in severity, frequency, or seriousness at any time during the study. In this case, it should be reported as an AE.

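### The SAP's treatment-emergent definition leaves out a pre-dose adverse event that becomes more frequent or serious on drug without a change in severity or relatedness, or that worsens after Day 28

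*SAP*

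**What the plan says.** SAP 3.6.1 gives the only definition of a treatment-emergent event in the two documents. It has two limbs: "AEs that occurred for the first time after the first dose of study drug or existed prior to the first dose and worsened", the second being limited to the treatment period. The next sentence restricts the second limb: "AE worsening applies to severity, or relationship to study drug". Frequency and seriousness are not named. Protocol 6.4 fixes the window: "The Treatment Period begins on Day 1 and concludes on Day 28".

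Protocol 8.1 sets the reporting rules. Events "will be monitored and documented from the time of informed consent until the Follow-Up Telephone Call", so an AE can start before dosing. For older conditions, "Any medical condition already present at the Screening Visit should be recorded as medical history and not be reported as an AE", unless the condition, or signs or symptoms, "present at baseline changes in severity, frequency, or seriousness at any time during the study". Relationship to study drug is not in that list.

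The protocol uses the term TEAE in 8.10 and 9.2.3 without defining it. Section 8.10 does say that the Screening examination is a baseline for assessing treatment-emergent events.

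**The concern.** Sites are told to report a change in frequency or seriousness, but the SAP gives such a change no route into the treatment-emergent tables when the event began before dosing and its severity and relatedness stay the same. Most rows of the safety overview, and the by-term tables built on them, are restricted to TEAEs or TESAEs. A pre-dose event that becomes more frequent and leads the patient to stop the drug would also be missing from the row and the targeted listing for TEAEs leading to study drug discontinuation.

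The time window is uneven as well. The limb for new events has no end date short of the end of AE collection, while the limb for worsening stops at Day 28. These tables describe the safety of a new formulation, and the SAP gives no reason for either restriction.

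**Working it through.** The documents state no figure on this point, so the check is a comparison of text, followed by test cases.

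**Attributes that count as a change**
- SAP 3.6.1 (worsening): severity, relationship.
- Protocol 8.1 (reportable change): severity, frequency, seriousness.
- Only severity is in both lists.

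**Window**
- New events under the SAP: after first dose, with AE capture through study completion. Protocol 10.3 includes the telephone contact in that.
- Worsening under the SAP: treatment period only, Days 1 to 28.
- Follow-Up Telephone Call: 7 days (±2) after the last dose. With a last dose on Day 28 that is Day 28 + 7 = Day 35, range Day 33 to Day 37. The gap is therefore about 5 to 9 days.

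**Test cases under the SAP wording**
1. AE with onset between consent and first dose, more frequent on drug, severity and relatedness unchanged: not a TEAE.
2. The same AE becoming serious on drug, severity and relatedness unchanged: not a TEAE, so not a TESAE. It remains in the row for any SAE, in the by-term table for that row (SAP 3.6.1 produces one for every overview category), in the SAE listing, and in the listing of all AEs (Protocol 9.2.3).
3. Pre-dose AE that worsens on Day 32, even in severity: not a TEAE. A new AE on Day 32 is a TEAE.
4. Pre-dose AE whose relationship changes from no to yes on drug: a TEAE, even with everything else unchanged.
5. AE that resolved before dosing and returns afterwards at the same severity, not judged related: left out if first-time occurrence is read literally, counted if the return is a new record judged by its own onset date. The SAP does not say which.
6. Medical-history condition that becomes more frequent or serious after dosing: under Protocol 8.1 it becomes an AE only then. It is a TEAE if that AE record is taken as the first occurrence, and not otherwise. The SAP does not say which.

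Cases 1 to 3 follow from the wording. Cases 5 and 6 are ambiguous, and two programmers could produce different tables.

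**Size**
- Planned patients per arm: 30 (Protocol 9.2.5). One patient misclassified = 1/30 = 3.3 percentage points of that arm's incidence.
- Pre-dose AE collection: 7 to 70 days by Protocol 3.1 (Protocol 6.2.1 puts the Screening Visit at least 29 days before dosing). The 70-day maximum allows for a 6-week washout.
- Neither document gives a rate of screening-period AEs or of changes in them, so a number of affected patients cannot be calculated.

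**The case against.** The strongest reply is that the two documents do not contradict each other. Protocol 8.1 decides when a condition present at Screening stops being medical history and becomes a reportable AE; it does not define treatment-emergence. A reader might infer that the SAP departs from a protocol definition of TEAE and that SAP section 5, which declares no changes from the protocol, is therefore wrong. The documents do not support that, because the protocol has no such definition. The point is a mismatch between a reporting rule and an analysis rule.

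A reader might also infer that the rule can only lower the counts. It cannot be said to do only that: the relationship criterion adds events that Protocol 8.1 does not list (case 4). For the same reason, removing that criterion would be a mistake, since it would take events newly attributed to study drug out of the TEAE tables.

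Three further replies narrow the gap. Many conditions present at Screening would enter through the first-occurrence limb once they change. Events that become serious stay visible elsewhere. Severity is graded by functional impact in Protocol 8.1.3, so an event leading to hospitalisation will often change grade too. Finally, the rule is the same in all three arms, the AE summaries are descriptive, and the laboratory shift tables and Hy's Law summary do not depend on TEAE status, so no bias between arms is shown.

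All of this stands, and it limits the size of the problem. It does not close the gap for AEs starting between consent and first dose. The all-SAE row mixes pre-dose and on-drug events because SAEs are collected from consent; the TESAE rows exist to separate them. For a non-serious event that becomes more frequent, only the listing of all AEs is certain to show it. The relationship route is narrow, because Protocol 8.1.3 reserves a yes for events with no other identifiable cause, and a pre-existing condition is an obvious other cause.

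**Conclusion.** The point holds for two groups. First, AEs with onset between consent and first dose that become more frequent or serious on drug, with severity and relatedness unchanged, are left out of the TEAE and TESAE counts. Second, pre-dose AEs that worsen between Day 28 and the follow-up call are left out, while new events in that week are counted. Recurrences and medical-history conditions are a matter of unclear wording. A reader might infer that they are certainly lost, but that needs a literal reading of first-time occurrence that the SAP does not impose.

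The number affected is probably small. That is a judgement, since the documents give no event rates. The 3.3 points per patient assumes that the safety population has the planned 30 per arm. The definition is still worth correcting before database lock, because Protocol 8.1 already requires these changes to be reported.

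**What to change.** Amend SAP 3.6.1 as follows:
- Define worsening as an increase in severity, frequency or seriousness, or a change in relationship to study drug. Keep the relationship criterion.
- Assess worsening from first dose through the Follow-Up Telephone Call, to match AE collection.
- Count as treatment-emergent any AE record with onset on or after first dose, including recurrences and medical-history conditions first reported as AEs after dosing.
- Derive TESAEs from this definition.

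The cost is SAP wording, minor programming and slightly higher TEAE counts. Protocol 8.1 needs no new reporting rule for this.
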